6.2 Statistical issues

6.2.1 Randomization

Randomization will be conducted centrally using Medidata Rave RTSM. The subjects will be allocated to 2 parallel groups receiving either levosimendan 1-2 mg daily or placebo in 2:1 ratio.

The estimated number of sites is approximately 100 and randomization will not be stratified by centre. Randomization will be stratified by the following factors:

1. Bulbar onset
2. Edaravone use
3. North American region

The stratification variable used to adjust the statistical models will combine all three randomization factors into a single factor with $2^3 = 8$ distinct levels.

Due to data entry errors at randomization, levels of the stratification factors used for randomization may differ from final CRF data. Primary analyses will be conducted with the levels of stratification factors used for randomization (STRATAR in ADSL), while final CRF data will be used in a sensitivity analysis (STRATAV in ADSL; see 7.5.4).

6.2.2 Significance level and confidence intervals

Two-sided tests with a significance level of 5% will be used throughout the analyses. Corresponding 95% confidence intervals will be calculated for model-based contrasts, comparing the active treatment to placebo, using model-based standard error estimates.

The study has interim analyses that allow early stopping for futility, but not for efficacy. Therefore, we do not make adjustments to the significance levels in the final analyses.

6.2.3 Multiplicity

No adjustment for multiplicity is planned.

Secondary endpoints will be tested hierarchically, in the following order:

1. Combined assessment of function and survival (CAFS) through 48 weeks
2. Time to respiratory event
3. Clinical Global Impression (CGI) through 48 weeks
4. Supine Borg CR 10 scale at 12 weeks
5. Slope of change in the ALSFRS-R respiratory domain through 48 weeks

See section 7.5.2 for more detailed descriptions of the endpoints and their methods of analysis.

6.2.4 Intercurrent events

Intercurrent events refer to events occurring after the start of study treatment that have an impact on the interpretation of or ability to collect measurements used to evaluate efficacy. For example, deaths and study discontinuations lead to missing data, study treatment discontinuation can cause a treatment effect to cease, or concomitant use of efficacious emergency medication can lead to misperceived efficacy of the investigational product.

In the primary efficacy analyses, missing data due to study discontinuations or deaths will be imputed following the procedure described in section 6.2.5 below. As specified in the study protocol, many endpoints are no longer collected after the end of study treatment. These missing

data points will also be handled following section 6.2.5. In these cases, missing data imputation attempts to estimate what could have happened, had the intercurrent event not occurred.

We do not consider there to be any relevant rescue medications to account for in the analyses. Baseline therapies of riluzole and edaravone are assumed to be stable for the course of the study, as required by the study protocol.

6.2.5 Dropouts and missing data

If a subject's data for a given planned visit is missing due to the actual visit having occurred outside the specified visit interval, data from the actual visit will be used for imputing data for the planned visit, if the time difference between the planned and actual visit no more than twice the tolerance for that visit. Otherwise, data will be imputed following the process for other types of missing data. See Figure 1 in section 2 for the visit timings and tolerance intervals.

In the primary evaluation, the flowing efficacy analyses will be conducted with missing data imputed using multiple imputation:

1. Supine slow vital capacity (SVC) through 12 weeks
2. Combined assessment of function and survival (CAFS) through 48 weeks
3. Time to respiratory event
4. Clinical Global Impression (CGI) through 48 weeks
5. Supine Borg CR 10 scale at 12 weeks
6. Slope of change in the ALSFRS-R respiratory domain through 48 weeks

For each imputed endpoint, 10 independent imputed data sets will be generated using the fully conditional specification (FCS) method. Predictive mean meatching will be used to impute continuous variables, and logistic regression methods for classification variables, as appropriate.

The imputation models will include measurements of the endpoint being imputed from all planned visits at which it should be collected, from the baseline visit up to the week 48 visit. The measurements are used in a one-row-per-subject format, by which all other visits' data are used to impute missing data at all visits. Further, the imputation model will also include time-invariant variables used in the statistical models or potentially associated with the missing outcome: treatment group, randomisation strata (site of onset, edaravone use, and region; as collected on the CRFs), sex, age group (< 65, 65–74, ≥ 75), and riluzole use status.

SAS code in the following fashion will be used to perform the imputation process:

```
proc mi nimpute = 10 seed = 270815;  
  class ARM STRATAV SEX AGEGR1 RILUZUSE;  
  var ARM STRATAV SEX AGEGR1 RILUZUSE AVAL1-AVAL8;  
  fcs regpmm (/ k = 5) logistic;  
run;
```

To ensure reproducibility of the imputation results, the randomly chosen seed value of 270815 will be used for all imputation procedures.

Imputation will be done directly based on the collected values, and derived quantities used for the analyses, like e.g. change from baseline, will be calculated after the imputation process,

within each imputed data set. For questionnaires that consist of multiple sub-items, values for individual items will be imputed, and the summary scores that are used for analysis purposes will be re-calculated based on the imputed data. Imputation is not done directly on the summary scores—which will have missing values if even one of their sub-items has a missing value—in order to maximise the use of collected information.

Multiply-imputed data will be analysed according to the methods specified for each endpoint in section 7, with the addition of performing the analysis separately in each imputed data set with the use of a by-statement in the analysis procedure. Results of all the analyses are then saved, and pooled estimates are calculated for inference purposes.

Pooled estimates of model parameters are to be obtained, depending on the analysis method, with SAS code in the following fashion:

```
proc mianalyze parms = parms covb(effectvar = rowcol) = covb;  
  class TRTP VISIT;  
  modeleffects TRTP VISIT TRTP * VISIT;  
run;
```

Above, the `parms` and `covb` data sets are obtained from the corresponding `solution` and `covb` outputs from the `proc mixed` procedure. The exact statements and options used for the pooling procedure will vary based on the analysis model used.

Model-based contrasts obtained with estimate statements will also be pooled, however the method used differs slightly from the one used for model parameters:

```
proc mianalyze data = estimates;  
  modeleffects estimate;  
  stderr stderr;  
  by label;  
run;
```

The method above will also be used to analyse hazard ratios from Cox models for time-to-event endpoints, with parameter estimates from `proc phreg` as the estimates data. For CAFS, Hodges-Lehmann estimates for median difference will be pooled in the same manner.

A complete-case analysis will be performed as a sensitivity analysis, using observed data only. There, listwise deletion will be used to select subject-visit records for fitting the model, removing subject-visits records from the analysis if any of the variables used contains a missing value.

Tipping point analyses will be considered for further evaluating sensitivity of the results with respect to missing data. In such an analysis, the distribution of missing data in the active treatment group would be shifted by varying amounts, until a point is found where the results of the analysis cross the threshold of statistical significance specified in section 6.2.2. The plausibility of a shift of the found size is then used to assess the robustness of results to unobserved differences due to missing data.

Subjects who discontinue study treatment but remain in the study can continue to contribute ALSFRS-R data, which will be included in the analyses where applicable. However, in time-to-

event analyses subjects will be censored from follow-up one day after study treatment discontinuation.

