Primary efficacy will be evaluated based on the fitted model, using contrasts to obtain an estimate of the difference between the treatment and placebo at the Week 12 visit (Visit 5). Statistical significance of the Week 12 treatment difference will be tested. All SVC measurements from planned study visits prior to the Week 12 visit will be included in the estimation of the model.

SAS code in the following fashion will be used to perform the computations:

```
proc mixed data = ADEFF order = data alpha = 0.05 covtest;
  where ITTFL = "Y" and PARAMCD = "SVCPPSUP" and
    AVISIT in ("Week 2", "Week 4", "Week 8", "Week 12");
  class TRTP(ref = "PLACEBO") AVISIT STRATAR USUBJID SITEID;

  model CHG = BASE STRATAR TRTP AVISIT TRTP * AVISIT / ddfm = KR;
  repeated AVISIT / subject = USUBJID type = UN R;
  random SITEID / type = VC;

  estimate "Treatment Difference at Week 12"
    TRTP 1 -1 TRTP * AVISIT 0 0 0 1 0 0 0 -1 / cl;
run;
```

In the primary analysis, missing data are imputed using multiple imputation. As a result, the analysis above is repeated for each of the imputed data sets with the use of a by-statement. The analysis results are then pooled for inference according to the methods described in 6.2.5.

In additional analyses, data from all planned visits through 48 weeks will be included in the MMRM, and the treatment effect will be estimated with contrasts at each study visit. Further, a random slope model will be fitted, with visits' actual study days replacing the visit factor.

Changes in SVC (supine) between the last measurement while on treatment and the post-treatment measurement from their End of Study visit will be described.

Subgroup analyses will be conducted by removing the randomization stratum effect from the primary analysis model, and including the subgroup term and its interaction with treatment.

Descriptive statistics of SVC (supine) will also be presented by visit, treatment group, and angle of measurement position. The angle is categorised into three groups: 1) completely flat (0 degrees); 2) slightly elevated (up to 15 degrees); 3) unable to perform supine (> 15 degrees). The effect of angle of measurement will also be explored in an additional analysis, where the angle will be included as a factor in the primary analysis MMRM.

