7.5.2 Secondary efficacy variables

The following secondary efficacy endpoints will be tested in the hierarchy below in order to preserve the overall alpha level:

1. Combined assessment of function and survival (CAFS) through 48 weeks
2. Time to respiratory event
3. Clinical Global Impression (CGI) through 48 weeks
4. Supine Borg CR 10 scale at 12 weeks
5. Slope of change in the ALSFRS-R respiratory domain through 48 weeks

The endpoints and their methods of analysis are described in the following sections. Endpoints and analyses that are not listed in the testing hierarchy are included for supportive purposes only.

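### Ten imputations with one seed leave avoidable Monte Carlo noise in any borderline confirmatory p-value, and raising the number costs only computing time

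*SAP*

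**What the plan says.** SAP 6.2.5 specifies, for each imputed endpoint, that "10 independent imputed data sets will be generated" by fully conditional specification, and the sample code repeats it: "proc mi nimpute = 10 seed = 270815". The seed is tied to reproducibility: "the randomly chosen seed value of 270815 will be used for all imputation procedures".

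The list of imputed analyses in 6.2.5 opens with "Supine slow vital capacity (SVC) through 12 weeks". The other five entries are the secondary endpoints of SAP 6.2.3 and 7.5.2: CAFS, time to respiratory event, CGI, supine Borg CR10 and the ALSFRS-R respiratory slope. For these, 7.5.2 says: "The following secondary efficacy endpoints will be tested in the hierarchy below in order to preserve the overall alpha level".

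Multiple imputation is the main analysis. SAP 7.5.1.1 says: "In the primary analysis, missing data are imputed using multiple imputation". On pooling, 6.2.5 says: "Results of all the analyses are then saved, and pooled estimates are calculated for inference purposes". Tests are two-sided at 5% (6.2.2).

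The SAP gives no reason for choosing 10, no target for Monte Carlo error, no rule for raising the number and no repeat under other seeds. Protocol 8.4.3 names multiple imputation but no number of imputations.

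**The concern.** A fixed seed makes the result reproducible, but not stable. It returns the same random draw each time, and another seed would have given another p-value. With 10 imputations the spread between seeds can be wide enough to move a result across 0.05.

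This matters most in the hierarchy. A chance miss at CAFS, the first step, blocks four later claims, and a chance pass opens them. Borderline results are plausible: SAP 5 plans about 80% power for CAFS and about 70% for time to respiratory event. A decision to claim or not claim an effect should not turn on a quantity that computing time can remove.

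**Working it through.** **Inputs.** From the SAP: m = 10 and seed 270815 (6.2.5); two-sided 5% (6.2.2); difference 3.6, SD 10, 164 evaluable per group at 1:1, 450 randomised 2:1 and about 20% dropout (5). FMI is not given and is assumed over 0.05 to 0.4.

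**The plan's own figure.** By normal approximation, n per group = 2 × (1.960 + 1.282)² × 10² / 3.6² = 162.2, so 163. The t-test gives 163.1, so 164, with 90.2% power. The sample size reproduces. With 450 × 0.8 = 360 evaluable at 2:1 (240 and 120), power is 89.5%, and the SE of the difference is 10 × √(1/240 + 1/120) = 1.12 points.

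**Noise between seeds.** With between-imputation variance B, the pooled estimate varies between seeds with SD √(B/m), which is √(FMI/m) in units of its SE. At m = 10 this is 0.07, 0.10, 0.14, 0.17 and 0.20 SE for FMI 0.05, 0.1, 0.2, 0.3 and 0.4. For supine SVC at FMI 0.2 it is 0.14 × 1.12 = 0.16 points.

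**Effect on the p-value.** Call the p-value under unlimited imputations the converged p. Each simulation cell used 400,000 draws with total variance scaled to 1 and W = 1 − FMI:

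- Q ~ N(z, FMI/m), with z = 2.054 for p = 0.04 and 1.881 for p = 0.06
- B ~ FMI × χ²(m−1)/(m−1)
- T = W + (1 + 1/m)B
- Rubin df = (m−1) × [1 + W/((1 + 1/m)B)]²

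Results at m = 10:

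| Assumed FMI | Converged p = 0.04: seeds giving p ≥ 0.05 | Converged p = 0.06: seeds giving p < 0.05 |
|---|---|---|
| 0.05 | 12% | 13% |
| 0.1 | 23% | 21% |
| 0.2 | 35% | 27% |
| 0.3 | 42% | 30% |
| 0.4 | 46% | 31% |

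At FMI 0.2, the central 95% of seeds reports a converged p of 0.04 anywhere from 0.018 to 0.091.

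The full calculation is needed. A shortcut using √(FMI/m) alone gives Φ((1.960 − 2.054)/0.141) = 25% for p = 0.04 at FMI 0.2, against 35%, because it ignores the noise in B, the 1 + 1/m factor and the df.

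**How often it bites.** Draw the converged z from N(1.960 + 1.282, 1) for 90% power or N(1.960 + 0.524, 1) for 70% power, and compare two seeds at m = 10:

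| Assumed FMI | Disagree on significance, 90% power | Disagree, 70% power |
|---|---|---|
| 0.05 | 1.5% | 3.0% |
| 0.1 | 2.3% | 4.5% |
| 0.2 | 3.7% | 7.0% |
| 0.3 | 5.2% | 9.6% |

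A converged p of 0.01 is lost in about 0.2% of seeds at FMI 0.2 and 1.5% at FMI 0.3.

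**Effect of a larger m.** Share of seeds reporting a converged p of 0.04 at or above 0.05:

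| m | FMI 0.2 | FMI 0.3 | FMI 0.4 |
|---|---|---|---|
| 10 | 35% | 42% | 46% |
| 100 | 4% | 10% | 15% |
| 200 | 0.7% | 3% | 7% |

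**The case against.** The case for leaving the plan alone has four parts.

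1. **Inference at m = 10 is sound.** Rubin's df and the 1 + 1/m factor allow for the finite number of imputations, and relative efficiency is about 98% at FMI 0.2 (1/(1 + 0.2/10)). This stands. A reader might infer that 10 imputations bias the estimate or inflate type I error, but nothing in the plan supports that.

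2. **The seed is fixed in advance.** This also stands. A reader might suspect room to choose a favourable seed, but 6.2.5 names a single value for every imputation procedure.

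3. **FMI may be low for several endpoints.** This largely stands. The roughly 20% in SAP 5 is a total dropout allowance, and Week 12 SVC is imputed from the subject's other visits through Week 48. ALSFRS-R collection can continue after treatment stops (Protocol 6.1.6, SAP 6.2.5). Time-to-event follow-up is censored one day after treatment discontinuation, so little may be imputed there. Week 48 CGI is more exposed, because off-treatment follow-up is meant for ALSFRS-R, ventilatory support and survival only. It is also tempting to cite SAP 7.10.3, which expects more missing data because of COVID-19. That statement mainly concerns Week 48 SVC. Protocol 6.6 collects ALSFRS-R, CGI and Borg at remote visits, so it is not general support for high FMI across the hierarchy.

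4. **A seed-free cross-check exists.** SAP 7.5.4.4 repeats every imputed analysis on observed data only. That helps, but it is a sensitivity analysis and does not replace the confirmatory p-value.

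These points limit the size of the problem. None is a reason to prefer 10.

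**Conclusion.** The point holds as a precision improvement, not as a flaw in validity. Ten imputations leave a borderline confirmatory p-value partly dependent on the seed. Even at an assumed FMI of 0.05 to 0.1, about 12% to 23% of seeds would turn a converged p of 0.04 into a reported miss, and the share grows with FMI. Across all possible results the risk is modest: about 1.5% to 5% of trials at 90% power and 3% to 10% at 70% power for FMI 0.05 to 0.3. The upper end of the 70% figure may not apply to time to respiratory event, where FMI is probably small.

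The number of imputations, the seed and the endpoints covered are stated in the SAP. The magnitudes rest on the assumed FMI range and on the normal-theory simulation above.

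**What to change.** In SAP 6.2.5, text and code, set nimpute to at least 100 for all six imputed endpoints, and preferably 200 or more where FMI is likely to be high, such as Week 48 CGI. Using 200 throughout would avoid having to judge FMI in advance. Keep the pre-specified seed. Report FMI and the Monte Carlo error with each pooled estimate. Make the change before the treatment code is opened.

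The cost is computing time: 10 times as many model fits at 100 and 20 times at 200. Sample size, data collection and the protocol text do not change, since the protocol names no number of imputations.

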6.1.6 Follow-up period for subjects who have discontinued the study medication

The subjects who have discontinued the study medication, but continue in the study, are encouraged to follow the study visit and phone call schedule according to the study protocol for recording ALSFRS-R, ventilatory support and survival status.

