5. DETERMINATION OF SAMPLE SIZE

Sample size estimation is based primarily on supine SVC results from the study 3119001 LEVALS (Table 1). LEVALS had placebo-controlled data only up to 2 weeks, and therefore extrapolation of the results was needed. The placebo effect from phase II tirasemtiv trial BENEFIT-ALS (Shefner JM et al., 2016) was also evaluated.

Assuming a difference of at least 3.6% in change from baseline supine SVC between treatment groups and a common standard deviation of 10%, 164 evaluable subjects per group in a 1:1 allocation ratio have 90% power to detect a statistically significant difference in a two-sided, 5% α -level, two group T-test. Using a 2:1 allocation ratio, randomisation of 450 subjects to the study (approximately 300 levosimendan and 150 placebo treated subjects) allows for a total dropout rate of approximately 20%.

Table 1. Mean (SD) change from baseline SVC (supine) %-predicted in LEVALS

Treatment	2 weeks	12 weeks
Levosimendan 1 mg x 2	+2.4 (8.3)	-4.9
Levosimendan 1 mg x 1	+0.8 (8.6)	
Placebo	-3.6 (9.4)	-17.7 ¹
Placebo (BENEFIT-ALS)	-1.4	-8.5

¹ Extrapolated from the data

SD = standard deviation

Based on the dexpramipexole phase III study EMPOWER (Cudkowicz ME et al., 2013), a 12 point reduction in total ALSFRS-R score and a 15% mortality rate at 12 months can be assumed

in placebo treated patients. Assuming a 10 point decline in ALSFRS-R, with a standard deviation of 8 points, and a 20% relative improvement in survival, 450 patients provide approximately 80% simulated power to detect a statistically significant difference using a joint rank test. With 450 subjects and assuming a 48-week levosimendan event rate of 73% and hazard ratio of 0.70, time to respiratory event has approximately 70% power to detect a statistically significant difference using a log-rank test.

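### The imputation of missing supine SVC leaves out baseline and on-treatment ALSFRS-R and NIV status, so the Week 12 difference can be biased if dropout differs by arm

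*SAP*

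**What the plan says.** SAP 6.2.5 sets one imputation scheme for the primary and the hierarchical secondary endpoints. "The imputation models will include measurements of the endpoint being imputed from all planned visits at which it should be collected", from baseline to Week 48. The other predictors are fixed over time: arm, strata, sex, age group and riluzole use. The PROC MI variable list agrees with the text. It contains no ALSFRS-R score, NIV status or progression rate.

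The omitted data exist:
- Protocol Table 1 schedules ALSFRS-R at baseline and Weeks 4, 8 and 12.
- Protocol 6.2.9 records NIV status at all visits.
- SAP 7.5.2.1 defines a baseline progression rate.

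After drug stop, Protocol 6.1.6 encourages subjects to keep the visit schedule "for recording ALSFRS-R, ventilatory support and survival status". SAP 6.2.4 notes that "many endpoints are no longer collected after the end of study treatment" and sends those gaps to the same imputation. It describes the aim as estimating the outcome as if the intercurrent event had not happened. SAP 6.2.5 adds that "Subjects who discontinue study treatment but remain in the study can continue to contribute ALSFRS-R data", but nothing places those data in the SVC imputation.

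SVC can also be missing while the subject is on drug: SAP 6.2.6 and 7.5.1.1 treat efforts graded unacceptable as missing.

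**The concern.** Multiple imputation rests on the assumption that, given the variables in the model, missingness is unrelated to the unseen value. A variable that predicts both dropout and SVC should therefore be in the model. SAP 6.2.5 accepts this principle, since it says it includes fixed variables that may relate to the missing outcome. Baseline ALSFRS-R and progression rate fit that description and are absent. Protocol 6.2.3 combines the ALSFRS-R respiratory items, NIV and low supine SVC in one endpoint meant to validate the SVC result, so the sponsor already treats these variables as linked.

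Different dropout reasons by arm are foreseeable. Protocol 4.5 requires treatment to stop for a defined heart-rate increase, and Protocol 1.1 reports that increased heart rate was more common on levosimendan in the earlier ALS study and led to discontinuations there. Stops for progression could weigh more heavily on placebo. Two subjects with the same earlier SVC, one worsening on ALSFRS-R and one stable, would receive imputed values from the same distribution. If such subjects drop out unevenly across arms, the error does not cancel in the treatment difference.

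**Working it through.** **1. The plan's own figure.** SAP section 5: "Assuming a difference of at least 3.6% in change from baseline supine SVC between treatment groups and a common standard deviation of 10" (percent), with "164 evaluable subjects per group in a 1:1 allocation ratio" for 90% power.
- Normal approximation: n = 2(1.960 + 1.282)² × 10² / 3.6² = 162.2, so 163 per group.
- Exact t-test power is 89.98% at 163 and 90.15% at 164. The stated 164 reproduces.
- At 2:1 with 20% dropout (240 and 120 evaluable), power is 89.5%. The standard error is 10 × √(1/240 + 1/120) = 1.12 points.

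**2. What has to be assumed.** SAP section 5 gives about 20% dropout in total, with no split by arm. Neither document gives a correlation between ALSFRS-R and SVC.

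**3. Equal rates, different reasons.** Assumptions:
- SD of SVC change 10; correlation r between ALSFRS-R change and SVC change.
- 20% missing in each arm: at random on levosimendan; on placebo with logit −1.55 − 0.8z, where z is standardised ALSFRS-R change.
- Under that logit, z is on average about 0.73 lower in placebo subjects with missing SVC than in those observed.

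If z is left out, the bias in the difference is approximately −p × SD × r × 0.73 × (1 − R²). Here p is the missing share and R² is the share of Week 12 variance explained by the SVC values that were seen.
- Only Week 4 SVC seen (0.35 × Week 12 change plus noise of SD 7): R² = 35² / (100 × 61.25) = 0.20.
- Week 8 SVC also seen (correlation 0.80 with Week 12): residual variance 1 / (1/100 + 0.35²/49 + 0.8²/36) = 33, so 1 − R² = 0.33.

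| Missing per arm | SVC seen before dropout | r = 0.3 | r = 0.5 |
|---|---|---|---|
| 20% | Week 4 | 0.20×10×0.3×0.73×0.80 = 0.35 | 0.58 |
| 20% | Weeks 4 and 8 | 0.20×10×0.3×0.73×0.33 = 0.14 | 0.24 |

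Simulation agrees: −0.34 to −0.37 and −0.58 to −0.60 in the first row across runs, and about −0.15 and −0.23 in the second. At 10% missing, the four values roughly halve, to −0.18, −0.30, −0.07 and −0.12. With z known for everyone and included, bias is below 0.02. In a run where the auxiliary was limited to values before drug stop, the bias without it was about −0.1 to −0.4, and adding it removed the bias.

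**4. Unequal rates, same reasons.** A multiple-imputation simulation used 450 subjects at 2:1, 10 imputations and 300 replicates per scenario. It assumed correlation 0.6 between earlier and Week 12 SVC, partial correlation 0.3 to 0.6 for the auxiliary, and dropout log-odds rising 1 to 2 per SD of worsening. Without the auxiliary, imputed SVC in dropouts was too high by 2.0 to 6.3 points. The effect on the difference was:
- 20% in both arms: about 0.
- 24% levosimendan, 12% placebo: +0.2 to +0.6.
- 28% levosimendan, 4% placebo: +0.5 to +1.4 (check: 2.01 × 0.24 = 0.48; 6.07 × 0.24 = 1.46).
- 16% levosimendan, 28% placebo: −0.2 to −0.7.

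With the auxiliary included, bias was within about 0.1 throughout.

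**The case against.** The strongest objection is the target. SAP 6.2.4 aims at the outcome without the intercurrent event and recognises that stopping drug may end its effect. ALSFRS-R and NIV recorded after stopping are off-drug information, and using them to impute on-drug SVC could carry the loss of effect into the estimate. This stands for post-stop data. It does not reach baseline values, values recorded before drug stop, or visits where SVC is missing on drug. The SAP gives no reason for leaving those out.

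A reader might infer that known respiratory decline is ignored because SVC is no longer measured after drug stop. The documents do not support that. Decline already visible in planned-visit SVC enters the model. Leaving out post-stop information is consistent with the stated target. One supine SVC is still taken at the end-of-study visit, 14–25 days after the last dose (Protocol Table 1 footnote and 6.1.5), although that visit is not in the imputation model either.

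The upper sizes also rest on favourable choices: only Week 4 SVC seen, 20% missing by Week 12, and ALSFRS-R known for everyone. With ALSFRS-R known in only half of the dropouts, bias of about −0.20 to −0.29 remains after the fix.

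The plan does have other checks: an observed-data analysis, a random slope model, an analysis setting post-NIV data to missing (SAP 7.5.4.11), and a tipping point analysis that is only to be considered. None brings ALSFRS-R or NIV into the prediction of missing SVC.

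**Conclusion.** The point holds as a gap in the imputation model, confirmed by both the SAP text and its code. It does not invalidate the primary analysis. With 20% missing per arm, different dropout reasons and correlations of 0.3 to 0.5, the bias is roughly 0.1 to 0.6 points. That is 3% to 17% of the 3.6-point effect (0.1/3.6 and 0.6/3.6), or at most about half a standard error (0.6/1.12). Unequal rates widen the range to about −0.7 to +1.4 points; matching rates and mechanisms bring it to about zero.

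A reader might also infer that the omission favours levosimendan, or that it favours placebo. Neither follows: the sign depends on dropout rates and reasons by arm, which the documents do not give. Sample size and the stated power are unaffected.

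**What to change.** In SAP 6.2.5, add auxiliary variables to the supine SVC imputation:
- baseline ALSFRS-R total and respiratory scores, and baseline progression rate;
- ALSFRS-R total and respiratory scores and NIV status at planned visits up to study-drug stop, including visits where SVC is missing on drug, for example for unacceptable quality.

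Use the same set for supine Borg CR10 and CGI. Treat ALSFRS-R and NIV values recorded after drug stop as unavailable in the primary imputation, say that this follows from the target in SAP 6.2.4, and add one sensitivity analysis that uses them.

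The cost is a longer variable list in PROC MI and one extra run. The FCS model becomes larger, already carries an eight-level stratum factor, and needs convergence checks. The ALSFRS-R auxiliaries will themselves be partly missing, and early NIV use may be too sparse to fit at every visit. The analysis model, endpoints and sample size stay as they are.
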